### 7.3.1 Stratification

Treatment allocation/randomization will be stratified according to the following factors:

Tumor type (NSCLC [PD-(L)1 refractory], CRPC, and MSS CRC)

# 7.4 Blinding

This is an open-label study; therefore, the Sponsor, investigator and participant will know the treatment administered.

## 7.5 Preparation/Handling/Storage/Accountability

## 7.5.1 Dose Preparation

Details on preparation and administration of navarixin (and pembrolizumab) are provided in the appropriate Pharmacy/Procedures Manual

## 7.5.2 Handling, Storage and Accountability

The investigator or designee must confirm appropriate temperature conditions have been maintained during transit for all study treatment received and any discrepancies are reported and resolved before use of the study treatment.

Only participants enrolled in the study may receive study treatment and only authorized site staff may supply or administer study treatment. All study treatments must be stored in a secure, environmentally controlled, and monitored (manual or automated) area in accordance with the labeled storage conditions with access limited to the investigator and authorized site staff.

The investigator, institution, or the head of the medical institution (where applicable) is responsible for study treatment accountability, reconciliation, and record maintenance (ie, receipt, reconciliation, and final disposition records).

For all study sites, the local country Sponsor personnel or designee will provide appropriate documentation that must be completed for drug accountability and return, or local discard and destruction if appropriate. Where local discard and destruction is appropriate, the investigator is responsible for ensuring that a local discard/destruction procedure is documented.

The study site is responsible for recording the lot number, manufacturer, and expiry date for any locally purchased product as per local guidelines unless otherwise instructed by the Sponsor.

04W5XD

**Product:** MK-7123 SCH 527123 **Protocol/Amendment No.:** 034-01

The investigator shall take responsibility for and shall take all steps to maintain appropriate records and ensure appropriate supply, storage, handling, distribution and usage of study treatments in accordance with the protocol and any applicable laws and regulations.

#### 7.6 **Treatment Compliance**

Interruptions from the protocol specified treatment plan for >12 weeks require consultation between the investigator and the Sponsor and written documentation of the collaborative decision on participant management.

# 7.7 Concomitant Therapy

Medications or vaccinations specifically prohibited in the exclusion criteria are not allowed. If there is a clinical indication for any medication or vaccination specifically prohibited, discontinuation from study therapy or vaccination may be required. The investigator should discuss any questions regarding this with the Sponsor Clinical Director. The final decision on any supportive therapy or vaccination rests with the investigator and/or the participant's primary physician. However, the decision to continue the participant on study treatment requires mutual agreement of the investigator, the Sponsor, and the participant.

Participants are prohibited from receiving the following concomitant therapies and vaccinations during the screening and treatment periods of the study:

- Immunotherapy not specified in this protocol
- Antineoplastic systemic chemotherapy or biological therapy not specified in this protocol
- Investigational agents not specified in this protocol
- Radiation therapy (radiotherapy for symptom management is allowed)
- Live vaccines within 28 days before the first dose of study treatment and while participating in the study. Examples of live vaccines include, but are not limited to, the following: measles, mumps, rubella, chickenpox, yellow fever, rabies, BCG, and typhoid vaccines. Seasonal influenza vaccines for injection are generally killed virus vaccines and are allowed. Intranasal influenza vaccines (eg. FluMist®) are live attenuated vaccines, and are not allowed.
- Glucocorticoids other than to modulate symptoms from an immune-mediated AE. Chronic systemic replacement doses of steroids and non-systemic steroids including inhaled steroids, topical steroids, intra-nasal steroids, intra-articular, and ophthalmic steroids are allowed.

There are no prohibited therapies after the Post-Treatment Safety Follow-Up visit.

### 7.7.1 **Rescue Medications and Supportive Care**

Participants should receive appropriate supportive care measures as deemed necessary by the treating investigator. Suggested supportive care measures for the management of AEs with potential immunologic etiology are outlined along with the dose modification guidelines in Section 7.2, (Table 4). Where appropriate, these guidelines include the use of oral or IV treatment with corticosteroids, as well as additional anti-inflammatory agents if symptoms do

Confidential 04W5XD

07WYDZ

Product: MK-7123 SCH 527123 Protocol/Amendment No.: 034-01

not improve with administration of corticosteroids. Note that several courses of steroid tapering may be necessary as symptoms may worsen when the steroid dose is decreased. For each disorder, attempts should be made to rule out other causes such as metastatic disease or bacterial or viral infection, which might require additional supportive care. The treatment guidelines are intended to be applied when the investigator determines the events to be related to pembrolizumab.

Note: If after the evaluation of the event, it is determined not to be related to pembrolizumab, the investigator does not need to follow the treatment guidance. Refer to (Table 4) in Section 7.2.1 for guidelines regarding navarixin dose modification and supportive care. Refer to Section 7.2.2 for pembrolizumab dose modification.

# **Supportive Care Guidelines for Pembrolizumab**

### **Pneumonitis:**

- For Grade 2 events, treat with systemic corticosteroids. When symptoms improve to Grade 1 or less, steroid taper should be started and continued over no less than 4 weeks.
- o For **Grade 3-4 events**, immediately treat with intravenous steroids. Administer additional anti-inflammatory measures, as needed.
- Add prophylactic antibiotics for opportunistic infections in the case of prolonged steroid administration.

### Diarrhea/Colitis:

Participants should be carefully monitored for signs and symptoms of enterocolitis (such as diarrhea, abdominal pain, blood or mucus in stool, with or without fever) and bowel perforation (such as peritoneal signs and ileus).

- All participants who experience diarrhea/colitis should be advised to drink liberal quantities of clear fluids. If sufficient oral fluid intake is not feasible, fluid and electrolytes should be substituted via IV infusion. For Grade 2 or higher diarrhea, consider GI consultation and endoscopy to confirm or rule out colitis.
- o For Grade 2 diarrhea/colitis that persists >3 days, administer oral corticosteroids.
- For **Grade 3 or 4 diarrhea/colitis** that persists >1 week, treat with intravenous steroids followed by high dose oral steroids.
- When symptoms improve to Grade 1 or less, steroid taper should be started and continued over no less than 4 weeks.

Type 1 diabetes mellitus (if new onset, including diabetic ketoacidosis [DKA]) or  $\geq$  Grade 3 hyperglycemia, if associated with ketosis (ketonuria) or metabolic acidosis (DKA):

- For T1DM or Grade 3-4 hyperglycemia
  - Insulin replacement therapy is recommended for Type 1 diabetes mellitus and for Grade 3-4 hyperglycemia associated with metabolic acidosis or ketonuria.
     Evaluate patients with serum glucose and a metabolic panel, urine ketones, glycosylated hemoglobin, and C-peptide.

MK-7123-034-01 Final Protocol 22-Mar-2018
Confidential

**Product:** MK-7123 SCH 527123 64

**Protocol/Amendment No.:** 034-01

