## **5.1.3** Dose Limiting Toxicity

Formal DLT evaluation will be performed at the interim safety analysis, following completion of one cycle of treatment by 10 evaluable participants in each dose arm. DLT nonevaluable participants will not be replaced. For example, if one of the first 10 participants in an arm is nonevaluable for DLT, then the next DLT evaluable participant enrolled and treated in the arm will be included in the interim safety analysis. The DLT evaluation period will be for one cycle (Day 1 to Day 21. Day 1 is considered the date a study drug was first administered and not the date of randomization if dosing did not occur on the date of randomization). During this time, supportive treatment with G-CSF will not be allowed.

An arm dose will be considered intolerable if >3 of 10 evaluable participants experience DLTs in Cycle 1. If the arm dose is not tolerated at 30 mg (and 100 mg), the arm may be discontinued and the protocol may be amended to include a lower navarixin dose.

All toxicities will be graded based on investigator assessment (Appendix 4 "Assessment of Intensity").

The occurrence of any of the following toxicities during Cycle 1 will be considered a DLT, if assessed by the investigator to be possibly, probably, or definitely related to study treatment:

- 1) Grade 4 non-hematologic toxicity (not laboratory)
- 2) Grade 4 anemia of any duration
- 3) Grade 3 anemia lasting >7 days or requiring transfusion
- 4) Grade 4 hematologic toxicity (other than anemia) lasting ≥7 days, except thrombocytopenia
  - a) Grade 4 thrombocytopenia of any duration
  - b) Grade 3 thrombocytopenia associated with bleeding
- 5) Grade 3 non-hematologic toxicity (not laboratory) lasting >3 days despite optimal supportive care.
- 6) Any Grade 3 or Grade 4 non-hematologic laboratory value if:
  - Medical intervention is required to treat the participant, or
  - The abnormality leads to hospitalization, or
  - The abnormality persists for >72 hours.

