### **General instructions:**

1. Corticosteroid taper should be initiated upon AE improving to Grade 1 or less and continue to taper over at least 4 weeks.

2. For situations where pembrolizumab has been withheld, pembrolizumab can be resumed after AE has been reduced to Grade 1 or 0 and corticosteroid has been tapered. Pembrolizumab should be permanently discontinued if AE does not resolve within 12 weeks of last dose or corticosteroids cannot be reduced to ≤10 mg prednisone or equivalent per day within 12 weeks.

3. For severe and life-threatening irAEs, IV corticosteroid should be initiated first followed by oral steroid. Other immunosuppressive treatment should be

initiated if irAEs cannot be controlled by corticosteroids.

Immune-related AEs	Toxicity grade or conditions (CTCAEv4.0)	Action taken to pembrolizumab	irAE management with corticosteroid and/or other therapies	Monitor and follow-up
Pneumonitis	Grade 3 or 4, or recurrent grade 2	Withhold  Permanently discontinue	Administer     corticosteroids (initial     dose of 1-2mg/kg     prednisone or     equivalent) followed by     taper	
 
Monitor participants for signs and symptoms of pneumonitis
 
Evaluate participants with suspected pneumonitis with radiographic imaging and initiate corticosteroid treatment
 
Add prophylactic antibiotics for opportunistic infections
 

Diarrhea / colitis	Grade 2 or 3	Withhold	Administer     corticosteroids (initial     dose of 1-2mg/kg     prednisone or     equivalent) followed by     taper	Monitor participants for signs and symptoms of enterocolitis (i.e. diarrhea, abdominal pain, blood or mucus in stool with or without fever) and of bowel perforation (i.e.
	Grade 4	Permanently discontinue		
 
peritoneal signs and ileus).
 
Participants with ≥ Grade 2 diarrhea suspecting colitis should consider GI consultation and performing endoscopy to rule out colitis.
 
Participants with diarrhea/colitis should be advised to drink liberal quantities of clear fluids. If sufficient oral fluid intake is not feasible, fluid and electrolytes should be substituted via IV infusion.
 

MK-7123-034-01 Final Protocol

Confidential

22-Mar-2018

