### **General instructions:**

- 1. Corticosteroid taper should be initiated upon AE improving to Grade 1 or less and continue to taper over at least 4 weeks.
- 2. For situations where pembrolizumab has been withheld, pembrolizumab can be resumed after AE has been reduced to Grade 1 or 0 and corticosteroid has been tapered. Pembrolizumab should be permanently discontinued if AE does not resolve within 12 weeks of last dose or corticosteroids cannot be reduced to ≤10 mg prednisone or equivalent per day within 12 weeks.
- 3. For severe and life-threatening irAEs, IV corticosteroid should be initiated first followed by oral steroid. Other immunosuppressive treatment should be initiated if irAEs cannot be controlled by corticosteroids.

Immune-related AEs	Toxicity grade or conditions (CTCAEv4.0)	Action taken to pembrolizumab	irAE management with corticosteroid and/or other therapies	Monitor and follow-up
Hyperthyroidism	Grade 2	Continue	Treat with non-selective beta-blockers (e.g. propranolol) or	Monitor for signs and symptoms of thyroid disorders.
	Grade 3 or 4	Withhold or permanently discontinue 	thionamides as appropriate	
Hypothyroidism	Grade 2-4	Continue	Initiate thyroid     replacement hormones     (e.g. levothyroxine or     liothyroinine) per     standard of care	Monitor for signs and symptoms of thyroid disorders.
Nephritis and renal dysfunction	Grade 2	Withhold	Administer corticosteroids	Monitor changes of renal function
	Grade 3 or 4	Permanently discontinue	(prednisone 1-2mg/kg or equivalent) followed by taper.	
Myocarditis	Grade 1 or 2	Withhold	Based on severity of AE administer	Ensure adequate evaluation to confirm etiology and/or exclude other
	Grade 3 or 4	Permanently discontinue	corticosteroids	causes

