# Hyperthyroidism or Hypothyroidism:

Thyroid disorders can occur at any time during treatment. Monitor patients for changes in thyroid function (at the start of treatment, periodically during treatment, and as indicated based on clinical evaluation) and for clinical signs and symptoms of thyroid disorders.

- o Grade 2 hyperthyroidism events (and Grade 2-4 hypothyroidism):
  - In hyperthyroidism, non-selective beta-blockers (e.g. propranolol) are suggested as initial therapy.
  - In hypothyroidism, thyroid hormone replacement therapy, with levothyroxine or liothyronine, is indicated per standard of care.
- o Grade 3-4 hyperthyroidism
  - Treat with an initial dose of IV corticosteroid followed by oral corticosteroids. When symptoms improve to Grade 1 or less, steroid taper should be started and continued over no less than 4 weeks. Replacement of appropriate hormones may be required as the steroid dose is tapered.

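### For diarrhea/colitis, Table 4 and Section 7.7.1 contradict each other on when corticosteroids start, and nothing says which text governs

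*Combined protocol and SAP*

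**What the plan says.** Section 7.7.1 opens by placing the suggested measures for immune-related events in Section 7.2 (Table 4). It then sets out its own event-by-event supportive care list for pembrolizumab. Both lists cover diarrhea/colitis.

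- **Table 4, diarrhea/colitis row:** "Diarrhea / colitis Grade 2 or 3 Withhold Administer corticosteroids (initial dose of 1-2mg/kg prednisone or equivalent) followed by taper". No persistence condition is attached.
- **Table 4, general instruction 3:** "For severe and life-threatening irAEs, IV corticosteroid should be initiated first followed by oral steroid". No wait is attached here either.
- **Section 7.7.1, Grade 2:** "For Grade 2 diarrhea/colitis that persists >3 days, administer oral corticosteroids".
- **Section 7.7.1, Grade 3 or 4:** an event "that persists >1 week, treat with intravenous steroids followed by high dose oral steroids".

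For hyperthyroidism, the Table 4 entry reads "Treat with non-selective beta-blockers (e.g. propranolol) or" and goes on to thionamides. Section 7.7.1 says at Grade 3-4: "Treat with an initial dose of IV corticosteroid followed by oral corticosteroids".

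Among the Cycle 1 dose-limiting toxicities in Section 5.1.3, criterion 5 is "Grade 3 non-hematologic toxicity (not laboratory) lasting >3 days despite optimal supportive care". The supportive care meant there is not defined. Section 5.1.3 calls a dose intolerable when more than 3 of 10 evaluable participants have a DLT in Cycle 1.

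**The concern.** A site treating Grade 3 colitis finds one instruction with no waiting period and another that makes intravenous steroids conditional on more than a week of persistence. Both are current protocol text. Two sites can each follow the protocol and treat the same event differently.

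DLT is a primary safety endpoint. It feeds the interim safety rule in Sections 5.1 and 10.7 and the between-arm difference in Section 10.6.2. Criterion 5 depends on how long a Grade 3 event lasts and on whether supportive care was adequate. If the protocol holds two accounts of that care, the criterion has no single standard to be judged against.

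**Working it through.** The plan states no DLT rate, no immune-related event rate and no operating characteristic for the 3-in-10 rule, so there is no figure to reproduce. The check is a side-by-side reading with day counts.

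**1. Start of corticosteroids, diarrhea/colitis**

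| Grade | Table 4 | Section 7.7.1 | Gap |
|---|---|---|---|
| 2 | no wait | after >3 days | more than 3 days |
| 3 | no wait; IV first if severe | IV after >1 week | more than 7 days |
| 4 | IV first (general instruction 3) | IV after >1 week | more than 7 days |

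The waits are minimums, so the gaps are lower bounds.

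**2. Precedence.** None is stated. The cross-references do not help: Section 7.7.1 cites Table 4 in Section 7.2.1 for navarixin dose modification, but the navarixin table is Table 3, and Table 4 belongs to Section 7.2.2.

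**3. Criterion 5 (threshold >3 days).** A related Grade 3 colitis lasting more than 3 and up to 7 days crosses the threshold before Section 7.7.1 calls for any steroid. Under Table 4 steroids are due without that wait, so the event may end sooner. It is also open whether a steroid-free course satisfies the supportive-care condition.

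**4. Grade 4.** Criterion 1 counts a related, non-laboratory Grade 4 event with no duration or supportive-care condition. It is a DLT under either text.

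**5. Criteria 9 and 10 can act the other way.** Table 4 requires a taper of at least 4 weeks (28 days) and lets pembrolizumab resume once the steroid has been tapered. Section 7.2.1 holds navarixin while pembrolizumab is held. Assume that resumption needs a completed taper and that navarixin is held from onset.

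- Criterion 10: Cycle 2 is due on Day 22, so a delay of more than 14 days means a start after Day 22 + 14 = 36. A taper begun on Day s ends no earlier than s + 28, which exceeds 36 when s is 9 or later.
- Criterion 9: 0.75 × 21 = 15.75 doses. A hold from Day 16 or earlier to Day 21 leaves at most 15 doses, which is below that.

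A Grade 2 event of 3 days or less receives steroids under Table 4 and none under Section 7.7.1. On these assumptions Table 4 could be the text that adds a DLT.

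**6. Sensitivity of the 3-in-10 rule (DLT rates p assumed).**

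- P(at least 4 of 10) = 1.3%, 12.1% and 35.0% at p = 10%, 20% and 30%.
- One participant's scoring decides the arm only when the other nine have exactly 3 DLTs: C(9,3) p³(1−p)⁶ = 84 p³(1−p)⁶ = 4.5%, 17.6% and 26.7% at the same rates.

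These figures show how close the rule can be to tipping. They do not size the colitis effect, which also needs the unknown chance that a participant has an event whose scoring turns on the steroid text.

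**7. Hyperthyroidism.** The Table 4 row names no steroid. The general instructions repeated above that row do: instruction 3 gives IV then oral steroid for severe and life-threatening events, and instruction 1 gives the taper of at least 4 weeks. Appendix 4 describes Grade 3 as severe and Grade 4 as life-threatening. Read whole, Table 4 can agree with Section 7.7.1, and the mismatch is between the row and its own header.

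**The case against.** The strongest reply is that Section 7.7.1 leaves supportive care to the treating investigator, calls the measures suggested, and does not forbid earlier steroids. One could read Table 4 as giving the dose and Section 7.7.1 the timing. The discretion is real, so the text does not dictate what every site does. The dose-versus-timing reading is stated nowhere, though, and general instruction 3 carries no wait. Section 7.7.1 also chooses its timing words: it treats Grade 3-4 pneumonitis at once but ties Grade 3-4 colitis to more than a week.

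A reader might infer four stronger things that the documents do not support:

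- **That the DLT count depends on which page a site follows.** The effect is conditional. For earlier steroids to avert a criterion 5 DLT, the event must end within 3 days with them and not without them, and nothing in the documents shows how often that happens.
- **That life-threatening events are scored differently.** Criterion 1 rules this out for non-laboratory events. For Grade 4 the concern is participant safety alone.
- **That Table 4 and Section 7.7.1 flatly contradict each other on Grade 3-4 hyperthyroidism.** Table 4's general instructions can supply the steroid and taper that its row omits.
- **That the comparison between arms is biased.** Both arms use the same text, and no differential effect is shown.

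It is also fair to say that the pneumonitis, hypophysitis, hepatic, renal and myocarditis guidance is broadly compatible between the two places.

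**Conclusion.** The contradiction on diarrhea/colitis stands, with start times more than 3 days apart at Grade 2 and more than 7 days apart at Grade 3 or 4, and no rule of precedence. It should be corrected on participant-safety grounds alone. The hyperthyroidism row is a lesser inconsistency, mainly within Table 4.

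An effect on DLT scoring is possible, not certain. Through criterion 5 it is confined to related, non-laboratory Grade 3 events in Cycle 1. Its direction is not fixed, because criteria 9 and 10 can act the other way if a completed taper is required before resuming. With no DLT or immune-related event rate in the documents, its size cannot be given. No view is taken here on which timing or agent is right.

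**What to change.** Reconcile Table 4 with the supportive care list in Section 7.7.1 so that each immune-related event has one consistent instruction, and state which text governs. Align the hyperthyroidism row with Table 4's general instructions and with Section 7.7.1. The clinical content is for the sponsor's medical team to decide.

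In Section 5.1.3, criterion 5, state that for immune-related events the supportive-care condition means care under the reconciled guidance. For other toxicities, leave it to investigator judgement: the guidance covers only immune-related events associated with pembrolizumab, whereas criterion 5 covers every related Grade 3 non-hematologic, non-laboratory toxicity.

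The cost is wording in the next amendment, with no added visits, procedures or participants.

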# Hypophysitis:

o For **Grade 2** events, treat with corticosteroids. When symptoms improve to Grade 1 or less, steroid taper should be started and continued over no less than 4 weeks. Replacement of appropriate hormones may be required as the steroid dose is tapered.

o For Grade 3-4 events, treat with an initial dose of IV corticosteroids followed by oral corticosteroids. When symptoms improve to Grade 1 or less, steroid taper should be started and continued over no less than 4 weeks. Replacement of appropriate hormones may be required as the steroid dose is tapered.

